Two-Step versus One-Step Sub-Retinal Injection

STUDY PROTOCOL

STUDY CENTRE

Save Sight Institute (SSI)
Department of Clinical Ophthalmology and Eye Health, University of Sydney
[name]
Campus of Sydney Eye Hospital (SEH)
[name]
Australia

PRINCIPAL INVESTIGATOR

Associate [name] Visiting Medical Officer Retinal Unit, Sydney Eye Hospital [name] Australia

[contact] Mob: [name]

Email: [contact]

Two-Step versus One-Step Sub-Retinal Injection

INVESTIGATOR SIGNATURE PAGE

I agree to implement and conduct this study diligently and in compliance with the protocol, good clinical practices and all applicable laws and regulations. I have read this protocol and I agree to all aspects. **Investigator Printed Name** Signature Date (Retain original in investigator site binder)

STUDY SUMMARY

Title Two-Step versus One-Step Sub-Retinal Injection

Primary Objective The study is aimed at assessing the reflux and retention of tPA

delivered by the one and two-step methods of sub-retinal injection

for the management of sub-retinal haemorrhage.

Study Design Randomised, controlled study in which patients diagnosed with

sub-macular haemorrhage and who have been scheduled for subretinal tPA and pneumatic displacement will be randomly assigned

to either the two-step or one-step group.

a) **Two-step injection:** In Step 1, 0.2mL of balanced salt solution will first be used to open the anatomical plane of the sub-retinal space. In Step 2, $50\mu g/0.1mL$ of tPA with 0.1mL of fluorescein

sodium at a concentration of 0.1mg/mL.

b) One-step injection: $50\mu g/0.1mL$ of tPA with 0.1mL of

fluorescein sodium at a concentration of 0.1mg/mL

Sample Size 20 participants with sub-macular haemorrhage

Eligibility Participants of age 18 years or above and who have a clinical

diagnosis of sub-macular haemorrhage of ≤ 7 days duration.

ABBREVIATIONS AND DEFINITIONS OF TERMS

AE Adverse Event

BCVA Best Corrected Visual Acuity

eCRF Electronic Case Report Form

GCP Good Clinical Practice

ICH International Conference on Harmonisation

IOP Intraocular Pressure

HREC Human Research Ethics Committee

OCT Optical Coherence Tomography

SAE Serious Adverse Event

tPA Tissue Plasminogen Activator

Table of Contents

IW	0-5	-Step versus One-Step Sub-Retinal Injection	1	
;	STU	UDY CENTRE	1	
]	PRINCIPAL INVESTIGATOR			
]	INVESTIGATOR SIGNATURE PAGE			
;	STUDY SUMMARY			
	ABBREVIATIONS AND DEFINITIONS OF TERMS			

Sub-retinal injection is a surgical manoeuvre used to deliver medications into the sub-retinal space. The sub-retinal space is a potential space and it has been argued that opening of the space should precede injection of therapeutic substances in order to accurately and precisely control the amount of delivered therapeutic substance.

In current clinical practice, the main indication for performing sub-retinal injections is the management of bleeding underneath the macula (sub-macular haemorrhage). To date, two principal approaches of delivering sub-retinal injections have been described, though little is known about the fate of substances injected into this space, beyond theoretical conjecture.

Broadly speaking, the two methods are:

- 1. A two-step approach, in which a physiologically insert fluid (balanced salt solution) is used to open the potential sub-retinal space, after which the therapeutic substance is injected (Simunovic et al., 2017).
- 2. A one-step approach, in which the therapeutic substance itself is used to create a limited iatrogenic retinal detachment, thereby opening up the sub-retinal space (Simonelli et al., 2010).

1.1 Rationale for performing the study

Researchers investigating emerging treatments, such as gene therapy, often overlook surgical variables in the delivery of substances in the sub-retinal space. This study will attempt to address this issue by studying the reflux of therapeutic substances delivered by the one- and two-step methods using the sub-retinal injection of tissue plasminogen activator (tPA) for the management of sub-macular haemorrhage.

The advantage of the one-step injection method is that it may be quicker than the two-step injection. The disadvantages are that there may be more wastage of medication, either due to the needle being in the incorrect anatomical plane (retinal layer) or because fluid may be more likely to regurgitate.

In order to compare these two methods, an inert fluorescent salt (fluorescein sodium) will be used to track the passage of the therapeutic drug Alteplase (Actilyse), a tissue plasminogen activator (tPA). In this study, the fluorescein will be directly injected under the retina.

Fluid samples will be taken from the eye at the completion of surgery to compare how much fluid has leaked during the surgical procedure. The samples are taken from the fluid-air exchange, a standard step

in vitrectomy surgery. Instead of discarding the fluid extracted, it will be instead collected. The total volume of fluid will be measured, as well as the concentration of fluorescein in this solution, using a fluorophotometer. Once measurements are taken, the fluid will be destroyed.

The procedure will be video-recorded in order to provide a means of subjectively assessing reflux at the time of injection of the tPA solution.

The results of this study may help determine the optimum approach in the delivery of treatments in retinal disease via sub-retinal injection in future studies.

1.2 Hypothesis

We hypothesise that the two-step approach will result in less reflux at the time of initiation of iatrogenic retinal detachment and during subsequent surgical steps.

2. Study Objectives

The overall objective of this study is to assess the reflux and retention of a therapeutic substance (tPA) delivered via two different techniques into the sub-retinal space to determine the optimum approach for sub-retinal injections.

3. Study Design

This is a randomised, controlled study in which patients diagnosed with sub-macular haemorrhage and who have been scheduled for sub-retinal tPA and pneumatic displacement will be randomly assigned (1:1) to either the two-step or the one-step group.

The target recruitment is 20 subjects. The sample size is based on the assumption that there is 10% (0.01mL) reflux of sodium fluorescein from blebs in both groups, and that there is a 60% wastage of fluid in the one-step procedure. The calculated sample size for a power of 0.80 and significance level of 0.05 is therefore 20 subjects.

We will review the results after the first 10 subjects. The trial will be terminated early if the appropriate statistical significance has been achieved (or in the event of a serious adverse event due to the study protocol).

Patients scheduled to undergo surgery for the displacement of sub-macular haemorrhage and who satisfy the eligibility criteria will be approached to participate in the study.

3.1 Study Group

- a) Two-step injection: In Step 1, 0.2mL of balanced salt solution will first be used to open the anatomical plane of the sub-retinal space. In Step 2, 50µg/0.1mL of tPA with 0.1mL of fluorescein sodium at a concentration of 0.1mg/mL.
- **b)** One-step injection: 50μg/0.1mL of tPA with 0.1mL of fluorescein sodium at a concentration of 0.1mg/mL

3.2 Endpoints

Primary Outcome

• The primary endpoint is the amount of refluxed fluorescein sodium between the two-step and one-step approach.

Secondary Outcomes

- Time taken to perform the sub-retinal injection.
- Change in visual acuity at 3 and 12 months

3.3 Involved Drugs

Two drugs will be used in this study – Alteplase (Actilyse) and Fluorescein Sodium (Fluorescite injection).

3.4 Quality Assurance

Standardised protocols have been developed for sub-retinal injection and assessment of sub-macular haemorrhage.

The major quality assurance features of the study are:

- Standardised eligibility and exclusion criteria
- Adherence to treatment protocol and follow-up
- Monthly meetings of personnel at the study centre to review methods and discuss problems

3.5 Organisational Structure of the Study Group

The centre will have trained BCVA and OCT examiners, a study co-ordinator and an ophthalmologist performing the surgery and sub-retinal injection.

4. Participant Eligibility

4.1 Participant Consent

Participants identified as being suitable will be asked if they are interested in participating in this study. The study requires that written informed consent is obtained from each participant prior to their enrolment in the study. The participant will be asked to sign the consent form only after an investigator has explained the purpose of the study, the participant has had time to read and understand the information sheet, has been given sufficient time to ask questions and agrees to participate voluntarily. The patient will be given a copy of the signed consent form to take home.

4.2 Eligibility of Participants into the Study

Patients will be approached at the time of consent for surgery. To participate in this study, the patient must meet all the following criteria:

4.2.1 Inclusion Criteria

- Participants will be patients with either a new or an established diagnosis of age-related macular degeneration and with a \leq 7-day history of vision loss secondary to sub-macular haemorrhage.
- Age ≥ 18 years (Participants with sub-macular haemorrhage or retinal arteriolar macroaneurysm are typically over 60 years of age.)
- Area of haemorrhage of greater than 1 disc area but not meeting the criteria for massive subretinal haemorrhage (haemorrhage extending beyond the temporal vascular arcades).
- Density of haemorrhage sufficient to obscure the RPE and choroidal detail.
- Haemorrhage involving the fovea.
- BCVA ≤ 6/60
- Written informed consent has been obtained

4.2.2 Exclusion Criteria

- Symptoms suggestive of sub-macular haemorrhage for > 7 days.
- Amblyopia in the study eye.
- Presence of another ocular disease affecting vision in the study eye.
- Known allergy to fluorescein
- Women who are pregnant, nursing or planning pregnancy or who are of childbearing potential and not using reliable means of contraception. (A woman is considered of childbearing potential unless she is post-menopausal and without menses for 12 months or is surgically sterilised)
- Participants unable to adhere to post-operative posturing.
- BCVA < HM
- Known allergy to agents used in the study e.g. fluorescein sodium
- Known history of significant cardio-pulmonary disease
- Multiple concomitant drug therapies in particular, beta-blockers (including eye drops)
- Patients who, in the opinion of the treating surgeon and anaesthetist, are unfit for a surgical procedure, with a condition that may put the patient at considerable risk, may confound the study results or may interfere significantly with the patient's participation in the study.

5. Entry into the Study

5.1 Patient Orientation

At presentation, patients are examined to determine whether they are eligible for the study.

A complete baseline examination is conducted (as part of standard of care) which includes the following:

- a) BCVA
- b) IOP measurement
- c) Slit lamp examination
- d) Fundus examination
- e) Central macular thickness by OCT

If they are deemed eligible, the investigator will discuss the study with the patient. They are informed of the possible risks and benefits of the study treatments. The patient either reads the detailed informed consent, or it is read to them. Any questions related to the study will be answered. The patient is allowed some time to consider the study prior to the consent form being signed.

5.2 Randomisation

After determining patient eligibility and signing the informed consent form (if the patient has agreed and is willing to participate in the study), each patient will be randomised to receive either two-step or one-step treatment. Randomisation will be performed using a random number generator in bit output (i.e. 0 vs 1). Patients will be sequentially assigned to either group according to the sequence of bits randomly generated (i.e. 0=1-step group, 1=2-step group). It is not anticipated that there will be a significant difference in outcome between the two arms of the trial. There is no placebo group.

6 Treatment

The surgical procedure will be identical to that undertaken in the routine management of significant sub-macular haemorrhage. The only difference between standard of care in the current study is that fluorescein sodium will be used to track flow of the tPA.

Following regional anaesthesia with sedation, the eye undergoing surgery and the periocular skin will be prepared with povidone iodine, after which a fenestrated sterile drape will be placed over the patient. Thereafter, a pars-plana vitrectomy will be undertaken in a routine fashion: after placement of a sterile lid speculum, 3 trans pars plana 25G ports will be placed infero-temporally, supero-temporally and superonasally. A core and limited peripheral vitrectomy will then be undertaken using the Alcon Constellation Vision System. At the completion of vitrectomy, sub-retinal injection of tPA will be undertaken as follows (either a. or b.), according to the group allocation. In each case, sub-retinal injection will be performed using the viscous fluid control mechanism of the Alcon Constellation Vision System and will be injected using viscous fluid control via a 25/38g teflon-tipped cannula. The site of initiation will be within an area of attached retina close to the region of sub-retinal clot. In each instance, the bleb will unite with the sub-retinal clot with the aim of its dissolution and displacement for therapeutic purposes.

Following peripheral search for retinal breaks, a fluid-air exchange will then be undertaken using a soft-tipped extrusion cannula. This is a standard step in this procedure, however, instead of discarding the fluid extracted in this manoeuvre, it will be collected. The total volume of fluid will be measured as well as the concentration of fluorescein in this solution using a fluorophotometer. Once measurements are performed, the fluid will be discarded.

The procedure will be video-recorded in order to provide a means of subjectively assessing reflux at the time of injection of the tPA solution. The video will be stored on an encrypted portable USB drive. The footage will be anonymous and will be deleted at the completion of the study.

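### Independent-bit randomisation of 20 patients holds 1:1 only on average: a modest power cost at the end, and a one-in-three chance of three or fewer patients in an arm at the 10-patient review

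*Protocol*

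**What the plan says.** Section 3 (Study Design) of the protocol states that patients "will be randomly assigned (1:1) to either the two-step or the one-step group". It adds "The target recruitment is 20 subjects" and "The calculated sample size for a power of 0.80 and significance level of 0.05 is therefore 20 subjects". It also plans a look that can end the trial: "We will review the results after the first 10 subjects". The level for that look is left at whatever significance is appropriate. Section 9 gives P = 0.01 as the level for ending early, to be applied at any point.

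Section 5.2 (Randomisation) fixes the mechanism: "Randomisation will be performed using a random number generator in bit output (i.e. 0 vs 1", and then "Patients will be sequentially assigned to either group according to the sequence of bits randomly generated". Zero means one-step and one means two-step. The protocol mentions no block, stratum, minimisation or limit on imbalance. Randomisation follows the eligibility check and signed consent. The protocol does not say who generates or holds the sequence, and no masking is described.

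**The concern.** Twenty independent bits are simple randomisation. In a large trial the imbalance would not matter. Here there are 20 patients and a review at 10, and nothing in section 5.2 secures equal arms at either count. Two things are at stake. One is power at the end, in a trial whose section 9 already concedes that the sample is small. The other is whether the review at 10 can do its job, since a comparison with two or three patients in one arm has little chance of supporting a decision to stop.

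This is not a detail left for an analysis plan to supply. The protocol states its own allocation mechanism, and that mechanism fits poorly with the ratio, size and review that the same protocol sets.

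**Working it through.** **Inputs.** From section 3: ratio 1:1, N = 20, review at 10, power 0.80, significance level 0.05 (sidedness not stated). From section 5.2: one bit per patient, used in order. From section 9: early termination at P = 0.01. Assumed: each bit is 0 or 1 with probability 0.5, as 1:1 implies.

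**The plan's own figure.** Section 3 assumes 10% reflux in both groups and 60% wastage in the one-step procedure. If the 60% is added to the 10%, the comparison is 10% v 70%. The two-sided, pooled two-proportion formula then gives

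n per arm = [1.96 × √(2 × 0.4 × 0.6) + 0.842 × √(0.1 × 0.9 + 0.7 × 0.3)]² / 0.6² = (1.358 + 0.461)² / 0.36 ≈ 9.2, rounded up to 10.

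That is 20 in total, which matches. It treats percentage volumes as response rates although the endpoint is an amount; that is a separate matter. The calculation presumes 10 per arm, a split the protocol implies but never writes.

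**Arm sizes at 20.** With the one-step count distributed Binomial(20, 0.5):
- exactly 10:10: 184,756 / 1,048,576 = 17.6%
- between 8:12 and 12:8: 73.7%
- 7:13 or worse: 275,960 / 1,048,576 = 26.3%
- 6:14 or worse: 11.5%
- 5:15 or worse: 4.1%

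**Power at 20.** No SD and no test are stated, so the effect is set to the standardised difference that gives 80% at 10:10 in a two-sided t-test, d = 1.325. Power comes from the noncentral t with n₁ + n₂ − 2 degrees of freedom and noncentrality d × √(n₁n₂ / (n₁ + n₂)).

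| Split | Power |
|---|---|
| 10:10 | 80.0% |
| 9:11 | 79.6% |
| 8:12 | 78.4% |
| 7:13 | 76.2% |
| 6:14 | 72.9% |
| 5:15 | 68.0% |

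Weighted by the binomial probabilities, the average is 77.8%. On the two-proportion basis above (10% v 70%), power is 83.8% at 10:10, 82–83% at 8:12 and 76–80% at 6:14, depending on which arm is smaller.

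**Arm sizes at the review.** With Binomial(10, 0.5):
- three or fewer in an arm: 2 × (1 + 10 + 45 + 120) / 1,024 = 352 / 1,024 = 34.4%
- two or fewer: 2 × (1 + 10 + 45) / 1,024 = 112 / 1,024 = 10.9%

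**What the review could show.** For an exact two-sided rank test, the smallest attainable p is 2 / C(10, k), where k is the size of the smaller arm. The last column is the power of a two-sided t-test at 0.01 with d = 1.325.

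| Split at 10 | Smallest exact rank p | t-test power at 0.01 |
|---|---|---|
| 5:5 | 2/252 = 0.0079 | 18.7% |
| 4:6 | 2/210 = 0.0095 | 17.8% |
| 3:7 | 2/120 = 0.017 | 15.2% |
| 2:8 | 2/45 = 0.044 | 11.1% |

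An exact rank test can therefore meet P = 0.01 only at 4:6 or better, and 34.4% of runs fall short of that.

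**With restricted lists.** Two permuted blocks of 10 give 5:5 at the review and 10:10 at the end. A block with m patients per arm has an expected 2m / (m + 1) allocations already fixed by those before them. For m = 5 this is 10/6 = 1.67 per block, or 3.3 over two blocks. Five blocks of 4 (m = 2) give 4/3 each, or 6.7 in all, with a worst split of 4:6 at the review and exactly 10:10 at the end.

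**The case against.** Simple randomisation is a legitimate method and the hardest to predict. Almost three-quarters of runs fall between 8:12 and 12:8, where power under the assumed effect is at least 78.4%, so most departures from 10:10 are harmless. A reader might infer from the 17.6% chance of 10:10 that the final analysis is badly underpowered. The figures do not support that: the average loss is about 2 points, and the 68% at 5:15 belongs to a region with a 4.1% chance. Nor does the 1:1 statement conflict with the bit sequence, which meets it in expectation.

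The review argument has limits too. No test is named, and section 3 does not tie its review to the 0.01 of section 9. With a t-test, 0.01 remains attainable at 3:7 and 2:8, though power is low at every split. Even at 5:5, an exact rank test meets 0.01 only when the arms separate completely, since the next p value is 4/252 = 0.016. A review that cannot stop the trial lets it run to 20, and section 9 allows stopping at other times.

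A reader might also infer that the study is unmasked, that the surgeon can see the list, and that sample handling must change as a result. The protocol describes no masking, but it does not say the study is unmasked, and it is silent on who holds the list. The arithmetic here concerns arm sizes only and supports no request about sample handling.

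Finally, blocking brings predictability. Section 4.2.2 gives the treating surgeon and anaesthetist a discretionary exclusion, so someone who could foresee an allocation might let it affect enrolment. That stands as a real cost of the remedy.

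These points reduce the weight of the concern. They do not remove it: the review remains unprotected by a mechanism the protocol itself fixes, and the protection is cheap.

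**Conclusion.** The concern holds as a point of efficiency. It is not a flaw in validity. At 20 patients the split is 7:13 or worse in 26% of runs, and average power falls from 80% to about 78%, on the assumption of a two-sided t-test with d = 1.325. The larger effect is at the 10-patient review, where 34% of runs have three or fewer patients in an arm and 11% have two or fewer. If an exact two-sided rank test were used and the 0.01 level of section 9 applied there, none of those runs could meet it, whatever the data. The arm-size probabilities assume only fair, independent bits. The statements on power and attainable p also depend on the test, which the protocol does not name.

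**What to change.** In section 5.2, replace the bit sequence with a restricted list. One suitable choice is two permuted blocks of 10, each 5:5, so that the allocation is balanced at the review and at the end. State that the block size is not disclosed to the surgeon and that each allocation stays concealed until the injection step. Section 6 already places the injection after the vitrectomy, so the surgical sequence need not change.

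The cost is one paragraph and a prepared list; N stays at 20. The downside should be stated openly: about 1.7 allocations per block (3.3 of 20) become fully determined for anyone who tracks earlier cases and knows the block size, which matters if the surgeon also judges eligibility. Opening the allocation in theatre does not hide an allocation that can already be deduced at enrolment, so withholding the block size is part of the remedy. Blocks of 4 would also work, but are more predictable (about 6.7 of 20 determined) and can leave 4:6 at the review.

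### Section 5.2 describes no concealment of the allocation sequence and fixes the arm at consent, although the arm is first needed when vitrectomy is complete

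*Protocol*

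**What the plan says.** Section 5.2 of the protocol contains the whole allocation procedure. Timing: "After determining patient eligibility and signing the informed consent form", each patient is randomised. Generation: "Randomisation will be performed using a random number generator in bit output (i.e. 0 vs 1"), with 0 meaning one-step and 1 meaning two-step. Assignment: "Patients will be sequentially assigned to either group according to the sequence of bits randomly generated".

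Section 4.2 places the approach to patients at the time of consent for surgery. The interval from there to the operation is not given.

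Section 6 shows when the arm is first used: "At the completion of vitrectomy, sub-retinal injection of tPA will be undertaken as follows (either a. or b.), according to the group allocation". Everything before that, from anaesthesia to the core and limited peripheral vitrectomy, is common to both arms.

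Section 3.5 lists trained examiners, a study co-ordinator and "an ophthalmologist performing the surgery and sub-retinal injection". It gives none of them custody of the sequence.

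Among the exclusions in section 4.2.2 is one resting on the opinion of the treating surgeon and anaesthetist. It reaches conditions that "may confound the study results or may interfere significantly with the patient's participation in the study". Another, for multiple concomitant drug therapies, has no threshold.

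**The concern.** Randomisation protects the comparison only if the person deciding on entry cannot know the next assignment. Section 5.2 says how the bits are produced and used, but not who holds them or whether they are hidden from the recruiter. Part of the entry decision is judgement, and section 1.2 states a directional hypothesis (less reflux with two-step). In that setting the protocol should close off foreknowledge explicitly.

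Timing is a second matter. The plan fixes the arm at consent, earlier than the surgery requires, and does not withhold it until needed. The operator may therefore know the arm during a vitrectomy meant to be the same in both groups. A patient whose operation stops before injection already counts as randomised but cannot supply the primary outcome, which comes from fluid collected after the injection.

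An analysis plan cannot supply these rules afterwards. Custody of the sequence and the moment of disclosure must be settled before the first patient is enrolled, and a bias at entry cannot be repaired once recruitment is over.

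**Working it through.** **1. What the text fixes and what it leaves open**

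| Step | Stated | Not stated |
|---|---|---|
| Generation (5.2) | random bits, 0 or 1 | who generates them; whether listed in advance or drawn one at a time |
| Custody (5.2, 3.5) | nothing | who holds the sequence; separation from recruiter and surgeon |
| Concealment (5.2) | nothing | envelopes, central release or any other device |
| Randomisation (5.2) | after eligibility and consent | interval to surgery |
| Disclosure (5.2, 6) | nothing | when the surgeon learns the arm |
| First use of the arm (6) | completion of vitrectomy | – |

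The last three rows show a gap between when the arm is fixed and when it is needed, with no rule on disclosure in between.

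**2. The plan's sample size, for scale**

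The point does not rest on the figure of 20, but the scale does. Section 3 gives 10% reflux in both groups, 60% wastage with one-step, power 0.80 and significance level 0.05. Reading these as proportions of 0.70 and 0.10, two-sided, with mean 0.40:

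n per arm = [1.960 × √(2 × 0.40 × 0.60) + 0.842 × √(0.70 × 0.30 + 0.10 × 0.90)]² / 0.60² = 1.819² / 0.36 = 9.19, rounded up to 10.

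The total is 20, as stated. Whether volume percentages should be treated as proportions is a separate question. Concealment does not change this number.

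One patient is 1/20 = 5% of the trial. At an even split, one patient who is randomised but not injected costs 1/10 = 10% of that arm's primary outcomes.

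**3. Can the next bit be guessed?**

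No block or stratum is stated. If the bits are independent, past assignments give a correct guess 50% of the time, which is no information. Foreknowledge therefore requires sight of the list or the generator. Fixed blocks of 4 would raise correct guesses to about 71% for someone who tracks past assignments, so small fixed blocks would not solve the problem.

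**4. Illustrative effect of a selection shift**

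Assumptions, none from the documents: a two-sample t-test, 10 per arm, no true effect, unchanged variance, and a shift of b standard deviations between arms caused by steering at entry. Degrees of freedom are 18, the critical value is 2.101, and the noncentrality is b × √(10/2) = b × 2.236.

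| b (SD) | Noncentrality | Two-sided type I error |
|---|---|---|
| 0 | 0 | 5.0% |
| 0.20 | 0.447 | 7.1% |
| 0.25 | 0.559 | 8.3% |
| 0.50 | 1.118 | 18.5% |
| 1.00 | 2.236 | 56.2% |

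For orientation, 2 patients of 10 in one arm, each with expected reflux 1 SD above average, give b = 2 × 1/10 = 0.20. The documents offer no basis for choosing a row.

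**The case against.** A reader might infer that the list is open, that the surgeon does know the arm throughout the vitrectomy, or that patients can be steered at will. The documents do not support this. Section 5.2 is silent on concealment, and silence does not establish an open list. The timing of randomisation is not the timing of disclosure. Assignment follows eligibility and consent, which is a partial safeguard, and independent bits cannot be guessed from earlier ones. The discretionary exclusion rests on the opinion of surgeon and anaesthetist, not the surgeon alone. What stands is narrower: the protocol describes nothing that would prevent foreknowledge.

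It can also be said that the steps closest to reflux are the injection and the fluid-air exchange, where the surgeon must know the arm whatever is done with envelopes, and that no particular vitrectomy step has been shown to alter reflux. Both remarks are fair and limit the gain. The primary endpoint ("The primary endpoint is the amount of refluxed fluorescein sodium between the two-step and one-step approach") is read by instrument, which limits reader bias, although it cannot undo selection at entry. The video, meant to "provide a means of subjectively assessing reflux at the time of injection of the tPA solution", has no masking described either, and later release of the arm does not address that.

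Finally, randomising between consent and surgery is ordinary practice, and the protocol gives no rate of operations that stop before injection. That loss is a possibility of unknown frequency. It still favours later release, which is better on all three counts at little cost.

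**Conclusion.** The point holds as a gap in the written procedure and an inexpensive improvement. Section 5.2 describes no concealment, no holder of the sequence independent of recruiter and surgeon, and no delay in disclosure. It also fixes the arm earlier than section 6 requires. The text therefore leaves three things possible: knowledge of the next assignment when eligibility is judged, knowledge of the arm during vitrectomy, and randomised patients without a primary outcome.

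The documents do not show that any of these will happen, and the size cannot be estimated from them. The rise in type I error from 5% to about 8% depends on an assumed 0.25 SD shift with 10 per arm and a t-test. The 10% loss per uninjected patient depends on an even split.

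**What to change.** Amend sections 5.2 and 6 as follows.

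- Name an existing team member who neither recruits nor operates to hold the sequence. The study co-ordinator would serve if that role takes no part in judging eligibility; section 3.5 does not give its duties.
- Keep the sequence in consecutively numbered, opaque, sealed envelopes, or have the holder release each assignment on request.
- Open the next assignment in theatre only when vitrectomy is complete and the surgeon confirms that the sub-retinal injection will go ahead. Eligibility and consent stay before surgery; no recheck of all the section 4.2 criteria during the operation is intended, since most could not be reassessed then.
- Log patients who do not reach injection as consented but not randomised.

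The cost is about one protocol paragraph and 20 envelopes. Materials for both arms must be ready in theatre, and there will be a short delay before the injection. The sample size stays at 20.
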